All subjects will be receiving background prednisone therapy. Subjects with relapsing/refractory GCA will have active disease despite previous or concurrent steroid therapy. Prednisone treatment must be initiated at Screening for subjects not currently receiving steroid treatment. An increase in prednisone dose may be required for some subjects currently receiving therapy to stabilize their disease activity prior to randomization. Investigators may consider if higher doses of prednisone are warranted for subjects with visual manifestations. The prednisone dose for all subjects at Screening will be determined by the Investigator and may be adjusted in an open manner based on the subject's disease status per investigator discretion. At Baseline (Randomization), doses must be within 20-60 mg prednisone for the starting dose when the pre-specified prednisone taper is initiated. Subjects will remain on the prednisone dose they are receiving at Baseline for one week and then will decrease the dose at Week 1 as specified in the taper regimen. Subjects will follow the open-label prednisone taper regimen until they reach a 20 mg dose of prednisone, when the blinded prednisone taper regimen begins. Subjects receiving a 20 mg prednisone dose at Baseline will continue the 20 mg dose for one week and at Week 1 will initiate the blinded taper.

Following the Screening period, eligible subjects will be randomized to receive sirukumab (100 mg SC q2w or 50 mg SC q4w) or matching placebo. All subjects will receive prednisone during the 52-week double-blind treatment period according to a pre-specified taper regimen. Randomization will be stratified by baseline oral prednisone dose ( $<30$  mg/day or  $\geq 30$  mg/day). The number of relapsing/refractory subjects will be capped at approximately 50% to ensure that a sufficient number of subjects with new onset disease are recruited.

An Independent Data Monitoring Committee (IDMC) will be utilized to ensure external objective medical and/or statistical review of safety issues in order to protect the ethical and safety interests of subjects and to protect the scientific validity of the study. The composition, remit, and procedures of the committee are provided in the IDMC charter.

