Prednisone for the unblinded (open-label) taper will be provided by the sites or by the Sponsor in certain countries in order to comply with local regulations. Use of standard release prednisone is required for the open-label taper. Prednisone doses between 60 and 20 mg will be administered during the unblinded (open label) taper. Subjects who reach 20 mg will receive the blinded prednisone from that visit. Prednisone doses below 20 mg and/or matching placebo will be provided in blister packs for blinded administration. Subjects should take their prednisone daily dose in one single daily administration in the morning.

	Study Treatment		
Product name:	Sirukumab	Placebo	Prednisone/ prednisone placebo
Dosage form:	1.0 mL Pre-filled syringe	1.0 mL Pre-filled syringe	Tablets
Unit dose strength(s)/Dosage level(s):	100 mg/mL or 50 mg/mL	--	Up to-60 mg/day
Route of Administration	SC	SC	Oral
Dosing instructions:	SC q2w (treatment arms A & B) SC q4w (treatment arm C)	SC q2w (treatment arms D & E)	20-60 mg/day open-label then 0-18 mg/day taper (blinded)

Note subjects randomized to treatment arm C will alternate between sirukumab 50 mg SC and matching placebo SC injections in order to maintain the blind (see Section 6.4).

Instructions for use of the SmartJect autoinjector will be provided to subjects and to the sites. Each step in the instructions is essential to ensure a successful delivery of study drug. It is important that the autoinjector is held against the skin at the injection site with sufficient force to disengage the safety interlock and make the push button actuatable, the actuation button is pressed to begin the injection cycle, and the autoinjector remains in place until the complete dose is delivered (second audible click or 15 seconds).

The investigator and designated site staff will be trained in the use of the SmartJect autoinjector for the SC administration of study drug. The trained site staff will be responsible for training each individual subject in the proper use of the SmartJect autoinjector. The study drug will be administered by the trained site staff during site visits until the subject is trained and confident in the use of the SmartJect auto-injector to self-administer study drug at home. If necessary a family member or carer will be trained in the use of the SmartJect autoinjector in order to administer the injection to the subject.

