## 6.3. Planned Dose Adjustments

No dose adjustment of sirukumab will be allowed in this study.

All subjects must be receiving prednisone (a minimum dose of 20 mg/day) at the start of Screening. Prednisone treatment must be initiated at Screening for subjects not currently receiving steroid treatment. A pre-specified prednisone tapering schedule outlined in [Table 1](#) begins for all subjects upon randomization at Baseline, (Week 0). The standardized prednisone taper regimen will be open-label with identical weekly decreases in dose according to the starting dose for all subjects, until subjects reach a dose of 20 mg/day. Thereafter, prednisone dosing will be blinded to allow the pre-specified differences in tapering.

Requirements for the prednisone taper are as follows:

- Subjects will remain on the prednisone dose they are currently receiving at Baseline (Week 0) for one week.

- At Week 1, the prednisone dose will be decreased in accordance with the pre-specified prednisone taper schedule (Table 1).
- The pre-specified maximum tapering schedule to be followed will depend on the subject's treatment group assignment.
- The prednisone taper will be unblinded (open-label) and will consist of identical weekly decreases in dose for all subjects until a dose of 20 mg/day is reached, at which point the blinded portion of the prednisone tapering regimen will commence.
- Subjects who are receiving a prednisone dose of 20 mg/day at Baseline (Week 0) should continue taking the open-label 20 mg daily dose for one week. At Week 1, these subjects will initiate the blinded taper regimen.

Subjects unable to follow the prednisone taper due to disease flare, adrenal insufficiency or safety reasons will cease the blinded prednisone treatment, and will be offered treatment with an investigator-defined open-label corticosteroid rescue regimen in combination with double-blind injections of sirukumab q2w or placebo q2w for the full 52 weeks. Subjects should continue to be followed per the protocol-specified assessments while receiving rescue treatment. There is no requirement for these subjects to be withdrawn from the study. When considering use of rescue prednisone, investigators should carefully assess whether the symptoms are related to an inflammatory GCA flare which would signify failure of tapering or is more likely due to non-inflammatory symptoms which could represent adrenal insufficiency or other co-morbidities.

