7.2. Study Treatments

7.2.1. Extent of Exposure

Listings of exposure to SC IP and prednisone study drug will be provided.

A summary of SC IP exposure will be provided. The following 3 parameters will be reported on the Safety set:

- Total number of injections a subject receives.
- Duration of SC IP treatment (weeks): defined as (Date of last SC IP dose – Date of first SC IP dose + 1 day) / 7. Only complete dates will be used when calculating duration of treatment. First and last injection dates will be used, regardless of any missed doses.
- Duration of SC IP exposure (weeks): defined as (Date of last SC IP dose – Date of first SC IP dose + 112 days) / 7, where 112 days corresponds to 16 weeks. Only complete dates will be used when calculating duration of exposure. First and last injection dates will be used, regardless of any missed doses.
- Cumulative SC IP dose: defined as the total dose in mg (SC IP or placebo) a subject receives.

A summary of prednisone study drug exposure will be provided. The following 2 parameters will be reported on the Safety set:

- Duration of prednisone study drug treatment (weeks): defined as (Date of last non-zero dose from the taper [i.e. the last prednisone end date from taper with a non-zero dose recorded] – Date of first dose from the taper + 1 day) / 7.
- Cumulative prednisone study drug dose (mg): defined as the total dose in mg a subject receives. For each week of the taper (both open-label and blinded), cumulative dose will be calculated as: the number of days x expected doses, the expected dose depending on the pre-specified taper schedule. Overall cumulative dose will be the sum of the cumulative doses of each week.

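### The protocol gives incompatible wording on the 20 mg prednisone step, and permitted starting doses such as 45 or 55 mg have no row in the taper table that SAP 7.2.1 relies on

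*Protocol*

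**What the plan says.** **Start of the blinded taper, for subjects coming down from a higher dose.**
- Protocol Section 6.1: "Subjects who reach 20 mg will receive the blinded prednisone from that visit".
- Section 6.3: the open-label decreases run "until a dose of 20 mg/day is reached, at which point the blinded portion of the prednisone tapering regimen will commence". Section 4.1 says the same in similar words.

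**Status of 20 mg.**
- Section 6.1 also says: "Prednisone doses between 60 and 20 mg will be administered during the unblinded (open label) taper". Its dosing row has 20 mg on the open-label side and 18 mg as the highest blinded dose ("20-60 mg/day open-label then 0-18 mg/day taper (blinded").
- On supply, Section 6.1 says: "Prednisone doses below 20 mg and/or matching placebo will be provided in blister packs for blinded administration".
- Table 1 lists 20 mg as the last open-label row. Its footnote makes each row a weekly step. The first blinded row is 15, 15 or 18 mg for the 3-, 6- and 12-month tapers.

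**Subjects already on 20 mg at Baseline.** Section 6.3 says they "should continue taking the open-label 20 mg daily dose for one week. At Week 1, these subjects will initiate the blinded taper regimen". The synopsis and Sections 4.1 and 4.2.1 agree. This explicit week is written for this group only.

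**Permitted starting doses.** Section 4.1 (repeated in 7.2) says that at Baseline "doses must be within 20-60 mg prednisone for the starting dose when the pre-specified prednisone taper is initiated". The open-label rows of Table 1, and of SAP Table 3, are 60, 50, 40, 35, 30, 25 and 20 mg.

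**Use in the SAP.** Section 7.2.1 builds cumulative prednisone study-drug dose, for open-label and blinded weeks alike, as days multiplied by expected dose, "the expected dose depending on the pre-specified taper schedule".

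**The concern.** A site reading the Section 6.1 sentence literally would move a subject to blinded product as soon as 20 mg is due. No blinded 20 mg exists, so that subject would go straight to 15 or 18 mg. A site reading Table 1 would give a week of open-label 20 mg first. The two sites would give different doses and start the blinded taper a week apart.

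A subject randomised on 45 or 55 mg meets the Baseline dose rule, but no passage says which row comes next. Sites must choose, and the SAP exposure formula has no expected dose to apply. Wherever the open-label dose given departs from the schedule, a formula that credits the schedule misstates exposure.

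At stake are consistency of dosing between sites and accuracy of the prednisone exposure summary. Sample size and power are not involved.

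**Working it through.** The plan states no figure for the 20 mg step, so the check is a comparison of passages and a count of weekly rows at 7 days each.

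**1. Cost of the omitted row.** Inputs are the Table 1 rows.
- Open-label rows: 60+50+40+35+30+25+20 = 260. Blinded rows sum to 34 (3-month), 116 (6-month) and 302 (12-month, Protocol Table 1).
- Totals from a 60 mg start, with the 20 mg row: 7×294 = 2058 mg, 7×376 = 2632 mg and 7×562 = 3934 mg, over 12, 26 and 53 weeks.
- Without the row, each falls by 7×20 = 140 mg and one week: 1918, 2492 and 3794 mg over 11, 25 and 52 weeks.
- SAP Table 3 has one fewer 4 mg row in the 12-month column, so its totals are 28 mg lower (3906 and 3766 mg). That is a separate discrepancy.
- Share of the 6-month total: 140/2632 = 5.3% from 60 mg. From 30 mg the total is 7×(30+25+20+116) = 1337 mg, and 140/1337 = 10.5%.
- Within the week itself the difference is 7×(20−15) = 35 mg for Arms A-D and 7×(20−18) = 14 mg for Arm E. The 140 mg is the difference once the taper is complete.

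**2. Whether there is a visit at which 20 mg is reached.** Weekly steps are counted from each listed start and compared with the early visits in Protocol Table 2 (Weeks 0, 2, 4 and 8).

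| Start (mg) | 20 mg reached at | Scheduled visit |
|---|---|---|
| 60 | Week 6 | no |
| 50 | Week 5 | no |
| 40 | Week 4 | yes |
| 35 | Week 3 | no |
| 30 | Week 2 | yes |
| 25 | Week 1 | no |
| 20 | Week 0 | yes |

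Four of the seven listed starts have no visit in the relevant week.

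**3. Starting doses without a row.** Of the nine multiples of 5 from 20 to 60 mg, only 45 and 55 are missing. To show the spread that the silence allows (illustrations only, no path is preferred):
- From 45 mg, joining at 40 gives 7×(45+40+35+30+25+20) = 1365 mg open-label over 6 weeks. Joining at 35 gives 7×(45+35+30+25+20) = 1085 mg over 5 weeks. The gap is 280 mg.
- From 55 mg, four conceivable paths run from 7×(55+40+35+30+25+20) = 1435 mg over 6 weeks to 7×(55+50+40+35+30+25+20) = 1785 mg over 7 weeks.

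**4. Where the schedule enters the analysis.** The days-times-expected-dose rule is in SAP 7.2.1, an exposure summary on the Safety set. The cumulative prednisone endpoint is in SAP 8.2.1, on the ITT set. That section refers to SAP 3.3 and 7.3 and to recorded doses, and it does not cite 7.2.1. SAP 3.3 names the Prednisone - Open Label eCRF page as the source for the open-label portion.

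**The case against.** The strongest reply is that the Section 6.1 sentence is being isolated. The sentence before it, the sentence after it, the dosing row and Table 1 all make 20 mg open-label, so the sentence may only mean that blinded packs are handed over at that visit. This is a reasonable reading, but the text does not say it, and Sections 4.1 and 6.3 also have the blinded taper itself begin when 20 mg is reached. The ambiguity stands. How many sites would act on the literal reading is unknown.

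Four stronger readings are tempting and are not supported.
- *Section 6.3 contradicts Section 6.1 for the same subjects.* The explicit open-label week in 6.3 is for those on 20 mg at Baseline. For subjects tapering down, 6.3 and 4.1 share the 6.1 wording. The conflict is with Table 1 and the dosing row.
- *The key secondary endpoint is credited from the schedule.* SAP 8.2.1 points to recorded doses and does not invoke 7.2.1. What can be said is that 8.2.1 separately summarises the study-drug component and does not rule out the 7.2.1 derivation.
- *The comparison between arms is biased.* The 20 mg step comes before the tapers diverge, the wording is the same for all five arms, and the completed-taper difference is 140 mg in each.
- *A missing visit leaves subjects without drug.* SAP 7.2.2.2 says each dispense lasts to the next scheduled visit plus a spare card, and it refers to a study procedure manual that is not available here. The absent visits show only that the wording of 6.1 cannot be applied literally for those starts.

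It is also fair to say that a 45 mg starter has lower rows to join, and that no document says how many subjects started between rows.

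**Conclusion.** The point holds as an inconsistency in the dosing text and a gap in one SAP derivation. If followed literally, the sentences that start blinded product on reaching 20 mg remove one 20 mg week: 140 mg and one week of schedule per subject who completes the taper. That assumes weekly rows as the Table 1 footnote states. Starting doses such as 45 or 55 mg are permitted but have no row, so the SAP 7.2.1 formula is undefined for those subjects until they join a listed row. It also misstates open-label exposure for anyone whose dose given differed from the schedule. The frequency of either case is not given.

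The consequence is limited to consistency of dosing and accuracy of exposure. SAP Sections 1.1 and 8 restrict efficacy to summary statistics after study termination, so no test result depends on this. No view is taken on which dosing rule is right.

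**What to change.** - **Protocol:** reconcile Sections 4.1, 6.1 and 6.3 with Table 1, so that one statement covers the 20 mg step and the start of blinded product for subjects tapering down, and does not depend on a visit that is not scheduled. Reconcile the permitted Baseline doses with the rows of Table 1.
- **SAP 7.2.1:** compute the open-label taper dose from the Prednisone - Open Label eCRF records and not from the expected schedule.
- **SAP 8.2.1:** state that the taper component uses the same recorded source.

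The cost is protocol wording and one changed derivation. It assumes the eCRF page holds dose with start and stop dates. SAP 7.2.1 supports this, since its treatment-duration definition already uses the end date of the last non-zero recorded taper dose. No new data collection is needed.

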## 6.2. Treatment Assignment

Central randomization will be implemented in this study. Subjects will be assigned to 1 of 5 treatment arms in accordance with the computer-generated randomization schedule generated prior to the start of the study, using validated software. Randomization will be performed by an Interactive Response Technology System (IRT). Randomization will be stratified by baseline oral prednisone dose ( $<30$  mg/day or  $\geq 30$  mg/day). Subjects will be randomized in a ratio of 3:3:2:2:2 to 1 of 5 treatment arms:

1. Treatment Arm A: Sirukumab 100 mg SC q2w for 52 weeks plus a pre-specified maximum of 6-month prednisone taper regimen (n=51)
2. Treatment Arm B: Sirukumab 100 mg SC q2w for 52 weeks plus a pre-specified maximum of 3-month prednisone taper regimen (n=51)
3. Treatment Arm C: Sirukumab 50 mg SC q4w for 52-weeks plus a pre-specified maximum of 6-month prednisone taper regimen (n=34)
4. Treatment Arm D: Placebo SC q2w for 52 weeks plus a pre-specified maximum of 6-month prednisone taper regimen (n=34)
5. Treatment Arm E: Placebo SC q2w for 52 weeks plus a pre-specified maximum of 12-month prednisone taper regimen (n=34).

Once a randomization number has been assigned to a subject, it will not be re-assigned.

## 6.3. Planned Dose Adjustments

No dose adjustment of sirukumab will be allowed in this study.

All subjects must be receiving prednisone (a minimum dose of 20 mg/day) at the start of Screening. Prednisone treatment must be initiated at Screening for subjects not currently receiving steroid treatment. A pre-specified prednisone tapering schedule outlined in [Table 1](#) begins for all subjects upon randomization at Baseline, (Week 0). The standardized prednisone taper regimen will be open-label with identical weekly decreases in dose according to the starting dose for all subjects, until subjects reach a dose of 20 mg/day. Thereafter, prednisone dosing will be blinded to allow the pre-specified differences in tapering.

Requirements for the prednisone taper are as follows:

- Subjects will remain on the prednisone dose they are currently receiving at Baseline (Week 0) for one week.

- At Week 1, the prednisone dose will be decreased in accordance with the pre-specified prednisone taper schedule (Table 1).
- The pre-specified maximum tapering schedule to be followed will depend on the subject's treatment group assignment.
- The prednisone taper will be unblinded (open-label) and will consist of identical weekly decreases in dose for all subjects until a dose of 20 mg/day is reached, at which point the blinded portion of the prednisone tapering regimen will commence.
- Subjects who are receiving a prednisone dose of 20 mg/day at Baseline (Week 0) should continue taking the open-label 20 mg daily dose for one week. At Week 1, these subjects will initiate the blinded taper regimen.

Subjects unable to follow the prednisone taper due to disease flare, adrenal insufficiency or safety reasons will cease the blinded prednisone treatment, and will be offered treatment with an investigator-defined open-label corticosteroid rescue regimen in combination with double-blind injections of sirukumab q2w or placebo q2w for the full 52 weeks. Subjects should continue to be followed per the protocol-specified assessments while receiving rescue treatment. There is no requirement for these subjects to be withdrawn from the study. When considering use of rescue prednisone, investigators should carefully assess whether the symptoms are related to an inflammatory GCA flare which would signify failure of tapering or is more likely due to non-inflammatory symptoms which could represent adrenal insufficiency or other co-morbidities.

**Table 1 Prednisone Taper**

	3 Month	6 Month	12 Month
Open-Label Taper	60	60	60
	50	50	50
	40	40	40
	35	35	35
	30	30	30
	25	25	25
	20	20	20
Blinded Taper	15	15	18
	10	13	17
	5	12	15
	3	10	15
	1	9	13
	0	8	10
	0	7	10
	0	6	10
	0	6	10
	0	5	9

	3 Month	6 Month	12 Month
	0	5	9
	0	4	9
	0	4	9
	0	3	8
	0	3	8
	0	2	8
	0	2	8
	0	1	7
	0	1	7
	0	0	7
	0	0	7
	0	0	6
	0	0	6
	0	0	6
	0	0	6
	0	0	5
	0	0	5
	0	0	5
	0	0	5
	0	0	4
	0	0	4
	0	0	4
	0	0	4
	0	0	4
	0	0	3
	0	0	3
	0	0	3
	0	0	3
	0	0	2
	0	0	2
	0	0	2
	0	0	2
	0	0	1
	0	0	1
	0	0	1
	0	0	1

\*Individual subjects will be receiving differing doses of prednisone at specified time points. Therefore, the tapering schedule indicates the required decrease in prednisone dose on a weekly basis, with the specific week varying by individual subject.

#### 6.4. Blinding

Blinding will be maintained during the 52-week double blind treatment phase of this study by the provision of sirukumab and matching placebo for sirukumab in pre-filled syringes in a matching presentation. Blinding to the prednisone dose during the taper will be maintained by providing prednisone dosages below 20 mg in numbered blister

packs. Depending on the subject's assignment to either the 3, 6 or 12 month taper, the over-encapsulated dose may or may not contain prednisone. The blister packs contain a combination of over-encapsulated 10 mg, 5 mg and/or 1 mg prednisone tablets with cellulose filler to prevent rattling and/or placebo capsules containing only the filler. Each patient, regardless of treatment arm, will be provided the same number of capsules per day for a given week to maintain the blind.

Blinding during the q4w dosing regimen will be maintained by the provision of placebo for sirukumab such that subjects randomized to this arm will follow a q2w dosing regimen but alternate between active (starting at baseline) and placebo treatments for the duration of the 52 week double-blind phase.

Investigators and the Sponsor/study team will remain blinded to the results of the fasting lipids, CRP and ESR laboratory tests after the start of treatment. Investigators and the study team will have access to Screening and Baseline values, and will thereafter remain blinded to these results until the end of Part A. Alerts will be provided by the central laboratory for abnormal, clinically significant findings to enable investigators to manage subject safety. Since the ESR is measured at the site, an unblinded assessor at the local laboratory will report the ESR results. The investigator will be notified of the value of the ESR result when an ESR value is > 40 mm/hr in order to determine if a treatment change is warranted. Investigators are advised to consider these notifications of an elevated ESR which has reached the alert value as an additional element in the determination of whether a subject is experiencing GCA disease flare. An elevated ESR in isolation should not be the sole basis for investigator assessment of disease flare, particularly in the absence of clinical symptoms (e.g., cranial or PMR) suggestive of disease activity.

An IDMC may carry out a futility assessment when approximately 30% of subjects have completed 52 weeks, dependent upon the recruitment rates. This committee will consist of clinicians and statisticians who are external to GSK in order to maintain the integrity of the blind during the 52-week double-blind treatment phase of the study.

The CEC, an independent committee composed of external specialists will be blinded to treatment assignment and will therefore not affect the integrity of the blind.

This will be a double-blind study and the following will apply:

- The investigator or treating physician may unblind a subject's treatment assignment **only in the case of an emergency** OR in the event of a serious medical condition when knowledge of the study treatment is essential for the appropriate clinical management or welfare of the subject as judged by the investigator.
- Investigators have direct access to the subject's individual study treatment.
- It is preferred (but not required) that the investigator first contacts the GSK Medical Monitor or appropriate GSK study personnel to discuss options **before** unblinding the subject's treatment assignment.
- If GSK personnel are not contacted before the unblinding, the investigator must notify GSK as soon as possible after unblinding, but without revealing the

treatment assignment of the unblinded subject, unless that information is important for the safety of subjects currently in the study.

- The date and reason for the unblinding must be fully documented in the CRF.

A subject may continue in the study if that subject's treatment assignment is unblinded but this must be discussed with the Medical Monitor.

